Opioid usage at 1, 24, 48, 72, and 96 hours after the block will be recorded by a member of the research team. Pain scores at rest and on movement (knee flexion) will be measured by the investigator using Visual Analog Scale (VAS). VAS will measure pain from a scale of 0-10. Nausea will be measured using a categorical scoring system (none=0; mild=1; moderate=2; severe=3). Nausea score will be reported by the patients. Anti-emetic usage will also be recorded. Sedation scores will also be assessed by a member of the study team using a sedation scale. Hospital length of stay (LOS) will be collected via EMR of the admission and discharge date to calculate the LOS. We will also measure time to first flatus, postoperative creatinine, incidence of hypotension (defined as BP decrease of more than 20% from morning of surgery), incidence of respiratory depression (defined by nursing report or naloxone use), and ambulation activity (anytime out of bed (up in chair, to bathroom and walking in hall with PT/nurse) will also be recorded daily. It will be recorded as yes/no.

All these parameters will be measured at 1, 24, 48, 72, and 96 hours after the cystectomy.

All patients will complete a phone survey approximately 6 months after surgery to assess for pain and how it impacts their daily function. This is meant to assess for the incidence of chronic post-op pain after cystectomy with all the different pain interventions. The survey will measure how their pain interfere with their general activity, mood, walking ability, normal work, relations with other people, sleep and enjoyment of life. If after four attempts to contact the patient are unsuccessful, the survey will not be completed; this will not be considered a deviation as the survey is not critical to the overall data collection.

Data management will include quality assurance and quality control measures. All collected data will be monitored by a data and safety monitoring group independent from the research team. Data quality, subject recruitment, accrual,-retention, outcome and adverse event data, assessment of scientific reports or therapeutic development, results of related studies that may impact subject safety and procedures designed to protect the privacy of subjects will be monitored at least annually.

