## **6.0 Study withdrawal/DC**

The patient can withdraw from the study at any time by contacting the research team or acute pain anesthesia resident. In such an event, patient may still have access to all the IV and oral pain medications. Anesthesia acute pain team will continue to follow the patient for 24 hours. After 24 hours, the anesthesia acute pain team will sign off and all further pain management will be done by the primary team.

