## **7.0 Statistical consideration**

Primary outcome: VAS score with movement at 48 and 72 hours

Primary Research Hypothesis: Thoracic epidural will provide lower postoperative pain scores compared to each of the other three methods used for cystectomy as measured by VAS scores at 24, 48, 72, and 96 hours under an enhanced recovery perioperative care pathway.

Secondary outcomes: Narcotic usage after 1, 24, 48, 72, and 96 hours. Pain scores using VAS at rest and on knee flexion at 1, 24, 48, 72, and 96 hours. Nausea scores at 1, 24, 48, 72, and 96 hours. Sedation scores at 1, 24, 48, 72, and 96 hours. Time to first flatus, postoperative creatinine, hospital length of stay (hospital length of stay (LOS) will be collected via EMR of the admission and discharge date to calculate the LOS), ileus, hypotension (defined as BP decrease of more than 20%), and ambulation/anytime out of bed (up in chair, to bathroom and walking in hall with PT/nurse) activity will also be recorded daily. It will be recorded as yes/no.

If the patient is discharged within 96 hours, every effort will be made to obtain data points, but we will not consider these data point deviations since our 96-hour data point will not change the integrity of the study.

Secondary Research Hypotheses: Thoracic epidural will show improved patient satisfaction scores and decreased nausea and sedation scores compared to each of the other three treatments.

Statistical analysis will be performed using a standard statistical program (SAS or SPSS). All data will be summarized (means, standard deviations, standard errors, and ranges for continuous variables; frequencies and percentages for categorical variables) by group. Demographic data will be compared between the four groups using ANOVA or chi-square tests as appropriate. The primary outcome, VAS ( Visual Analog Scale) at 48 and 72 hours, will be compared between the

groups using repeated measures ANOVA; the model will include fixed effects for group, time, and the group by time interaction and random effects to allow correlations between the two times and different variances for the two times.

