Pain and satisfaction scores and opioid usage over time will be analyzed using repeated measures ANOVA. Nausea and sedation scores will be compared between groups at each time point using Mantel-Haenszel chi-square tests for ordered categorical data. Time to first flatus, postoperative creatinine, and LOS will be compared between the groups using one-way ANOVA. The binary outcomes of incidence of ileus, hypotension (defined as BP decrease of more than 20%), and incidence of respiratory depression will be analyzed using logistic regression. Distributions of the continuous variables will be examined, and a transformation of the data (e.g. natural logarithm) or nonparametric tests will be used as necessary. A 5% significance level will be used for all comparisons.

Based on prior studies, the coefficient of variation for the VAS ( Visual Analog Scale) score at 48 and 72 hours is estimated to be 0.70. With a sample size of 40 per group the study will have 80% power to detect a ratio of means of 1.5 for VAS score between any two of the four treatment groups, assuming two-sided tests each conducted at a 5% significance level.

All patients will receive a phone survey approximately 6 months after surgery to assess for pain, quality of life, and satisfaction of hospital stay. Quality of life is measured by how their pain interferes with their general activity, mood, walking ability, normal work, relations with other people, sleep and enjoyment of life. If after four attempts to contact the patient are unsuccessful, the survey will not be completed; this will not be considered a deviation as the survey is not critical to the overall data collection.

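### Cheap improvement: the primary model uses only the 48 h and 72 h movement scores, so the other scheduled scores cannot support it when both primary readings are missing

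*Combined protocol and SAP*

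**What the plan says.** Section 7.0 states "Primary outcome: VAS score with movement at 48 and 72 hours". For the primary analysis, "the model will include fixed effects for group, time, and the group by time interaction", together with "random effects to allow correlations between the two times and different variances for the two times". Two times enter the model, and no other pain score does.

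The same score is taken more often. Study procedures (under 4.0) says "All these parameters will be measured at 1, 24, 48, 72, and 96 hours after the cystectomy", and the secondary outcomes in 7.0 include "Pain scores using VAS at rest and on knee flexion at 1, 24, 48, 72, and 96 hours". Sections 1.0 and 2.0 list VAS at 24, 48, 72 and 96 h without the 1 h reading, so 1 h is not consistently scheduled. The 24 h reading appears in every list.

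A later sentence in 7.0 says "Pain and satisfaction scores and opioid usage over time will be analyzed using repeated measures ANOVA". It does not list the times, but the remaining readings are evidently meant to be used there.

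On missing scores, 7.0 says only "If the patient is discharged within 96 hours, every effort will be made to obtain data points", and justifies this by reference to the 96 h point. Section 6.0 says "The patient can withdraw from the study at any time". No analysis set, imputation rule or sensitivity analysis is given for missing 48 or 72 h scores.

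**The concern.** A likelihood-based model uses every score it contains to inform the means at 48 and 72 h. In a two-time model, a patient with neither reading (for example after withdrawal on the first day) has no part in the primary analysis, even with a recorded 24 h score. A patient with one of the two readings stays in if the model is fitted by likelihood, as the random-effects wording suggests. A classical repeated measures ANOVA would drop that patient as well, and the plan does not say which fit is meant.

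Two things are at stake. The first is a little precision. The second is possible bias: loss that depends on 24 h pain is ignorable under likelihood when the 24 h score is in the model, and in general not when it is left out.

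**Working it through.** **1. The plan's own figure.** Inputs from 7.0: coefficient of variation 0.70, ratio of means 1.5, 40 per group, two-sided 5%.

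- Log-scale SD = √ln(1 + 0.70²) = √ln 1.49 = 0.631.
- Log-scale difference = ln 1.5 = 0.405. Planned effect = 0.405 / 0.631 = 0.64 SD.
- Noncentrality = 0.405 / (0.631 × √(2/40)) = 2.87. Power is 80.9% by noncentral t with 78 df, and 81.9% by the normal approximation.

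The stated 80% is reproduced, provided all 40 per group contribute. With 39 it is 79.9%, and with 36 it is 76.6%. Section 4.0 randomises exactly 40 per group, with no allowance for loss.

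**2. Precision.** Let q be the share missing both primary readings and ρ the correlation with the 24 h score. The documents give neither, so both are assumed. If the 24 h score is seen in everyone and loss is at random, adding it gives

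effective n = 40 / [(1 − ρ²)/(1 − q) + ρ²].

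Example: q = 10%, ρ = 0.5 gives 40 / (0.75/0.90 + 0.25) = 36.9, against 36 in the two-time model.

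| q | Two-time power | With 24 h, ρ = 0.3 / 0.5 / 0.7 | Gain (points) |
|---|---|---|---|
| 0% | 80.9% | 80.9 / 80.9 / 80.9% | 0 |
| 5% | 78.9% | 79.1 / 79.4 / 79.9% | 0.2 to 1.0 |
| 10% | 76.6% | 77.0 / 77.7 / 78.7% | 0.4 to 2.1 |
| 20% | 71.5% | 72.3 / 73.8 / 76.0% | 0.8 to 4.5 |

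**3. Bias when loss differs by arm.** Assumptions: no true difference; equal correlation ρ between readings; 7%, 13% or 19% of the epidural arm lost before 48 h against 2% of the comparator; log-odds of loss rising by 1 per SD of 24 h pain; a further 8% lost at random at 72 h. The contrast is the mean of 48 and 72 h. Then

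bias = ρ × D,

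where D is the between-arm difference in mean 24 h score, in SD, among patients still observed. Large-sample simulation gives D of about 0.05, 0.10 and 0.14.

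- ρ = 0.5: bias about 0.02, 0.05 and 0.07 SD.
- ρ = 0.7: bias about 0.03, 0.07 and 0.10 SD.

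With the 24 h score in the model, the bias is below 0.01 SD throughout. Relative to the planned effect, 0.02/0.64 = 3% and 0.10/0.64 = 16%. The complete-data standard error of this contrast is √((1 + ρ)/40), or 0.19 to 0.21 SD. The worst case is therefore 0.10/0.206 = 0.49 standard errors, for a type I error of about 7.7% in place of 5%.

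**4. Direction.** In step 3 the epidural arm loses more of its high-pain patients, so the error favours the epidural. Reversing this, with a true log ratio of 0.405, no loss in the epidural arm and 10% to 20% in the comparator, the 48 h estimate falls to between 0.389 (10%, ρ = 0.3) and 0.328 (20%, ρ = 0.7). That is a shrinkage of 4% to 19%. With 24 h included it is 0.400 to 0.406. With 10% lost in both arms by the same mechanism, the two-time estimate is 0.401 to 0.404, so no bias is visible.

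**5. Is the larger model feasible?** Covariance parameters: 2 × 3/2 = 3 for two times, 4 × 5/2 = 10 for four, 5 × 6/2 = 15 for five. In 600 simulated trials with four arms of 40, the five-time unstructured model could be fitted with no loss of precision, and it removed the bias in step 3. With 10% loss in both arms it changed the estimate by less than 0.005 SD and its spread by about 2%.

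**The case against.** Matching the model to the two declared primary times is a legitimate and simple choice, and much of the defence stands. Section 1.0 gives an average inpatient stay of 7 days, so most patients should be in hospital at both times and missing both readings should be uncommon. Equal loss leaves almost nothing to correct. The bias in step 3 needs loss that is both unequal and tied to 24 h pain, which is the mechanism the larger model handles best.

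A reader might infer three stronger things, and the documents support none of them:

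- **That the plan expects 48 and 72 h scores to go missing.** The discharge sentence is justified by the 96 h point alone, and 6.0 permits withdrawal without giving a rate.
- **That the primary result will be biased towards the epidural.** No text supports unequal loss or says which arm would lose more. The arms do differ visibly (a preoperative catheter against end-of-case injections), which makes unequal loss possible but does not establish it.
- **That the other readings are thrown away.** They are left out of the primary model only. 7.0 has a separate analysis of pain over time. Two estimates of the same scores are not a conflict when one is labelled primary.

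What survives is narrower. Nothing in the plan protects the primary contrast if such loss occurs, and the data that would do so are already being collected.

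**Conclusion.** This is a cheap improvement, not a flaw that threatens the trial. It changes nothing with complete data and little with low or balanced loss. Its main value is insurance: if loss depends on 24 h pain and differs by arm, the two-time contrast is off by about 0.02 to 0.10 SD under the assumptions in step 3, and using the 24 h score removes nearly all of that. The loss rates, the correlations and the link to 24 h pain are all assumed, so the figures show what could happen, not what to expect. The textual finding is firm: two times in the primary model, at least four scheduled, and no rule for missing scores.

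**What to change.** In 7.0, replace the two-time primary model with one along these lines: *Movement VAS at all scheduled post-operative times will be analysed in one repeated measures model fitted by REML, with group, time, group by time and an unstructured covariance matrix. All randomised patients with at least one score will be included. The primary epidural contrasts are those at 48 and 72 h.*

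Use at least 24, 48, 72 and 96 h. Add 1 h if it is to be collected, and bring 1.0 and 2.0 into line with Study procedures on that point. Enter the 1 h and 24 h scores as outcomes, not covariates, because they are measured after treatment. Naming REML also settles whether a patient with one primary reading is kept. The same model can serve the secondary analysis of movement pain over time.

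The cost is one sentence, no new data, and 10 to 15 covariance parameters in place of 3, which 160 patients support. The change does not help patients with no reading at all, or correct for loss driven by later, unobserved pain. Those cases still need a stated missing-data approach and a sensitivity analysis.

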## 2.0 Rational and Specific Aims

All of the pain control modalities in this study have been used as postoperative analgesia in prior studies. The specific aim of this study is to compare the difference between the pain control methods in achieving the following:

1. Decreased opioid requirements
2. Improved postoperative VAS (Visual Analog Scale) pain scores
3. Decreased opioid side effects (Nausea, sedation, ileus, respiratory depression)
4. Decreased hospital length of stay (LOS)

The primary endpoint of this study will be VAS (Visual Analog Scale) pain score at both resting and with movement. The VAS Visual Analog Scale) pain score will be measured at 24, 48, 72 and 96 hours under an advanced recovery perioperative care pathway.

The secondary endpoint includes intravenous opioid consumption, opioid side effects (nausea, sedation, ileus, respiratory depression), and LOS. Hospital length of stay (LOS) will be collected via EMR of the admission and discharge date to calculate the LOS. The IV and PO opioid doses will be quantified at 1, 24, 48, 72, and 96 hours. All the opioid consumption (both PO and IV) will be converted to PO morphine equivalent for analysis. We will also measure postoperative nausea and sedation scores at 1, 24, 48, 72, and 96 hours. Nausea will be measured on a 4-point scale: none, mild, moderate or severe. This is collected as patient reported as well as per nursing documentation. Sedation score is also reported on a 4-point scale: awake/alert, quietly awake, asleep/arousable or deep sleep. This is collected as an observation by nurse coordinator/staff. We will access patient's satisfaction at 24, 48, 72 and 96 hours. This will be measured on a 5-point scale; very unsatisfied, unsatisfied, neutral, satisfied and very satisfied. We will also measure time to first flatus, postoperative creatinine, incidence of hypotension (defined as BP decrease of more than 20%), incidence of respiratory depression, and ambulation activity.

Ambulation is defined as anytime out of bed (up in chair, to bathroom and walking in hall with PT/nurse) activity will also be recorded daily. It will be recorded as yes/no.

---

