### **4.0 Enrollment/Randomization**

All cystectomy cases scheduled by the urologists at IU Health University Hospital will be identified. Subjects will be contacted face-to-face prior to surgery by one of the research team members. They will be informed about the study and all questions will be answered. The potential subjects will be given a copy of the informed consent form and authorization form. The subjects will then be contacted face-to-face in POCU on the day of surgery and if participation is agreed, written consent will be taken. All patients will undergo a standardized enhanced recovery perioperative care pathway designed and agreed upon by the perioperative team of anesthesiologists and surgeons.

A total of 160 subjects will be randomized by a computer program into four groups (40 in each group):

1. Thoracic epidural– epidural bupivacaine 0.05%/hydromorphone 0.05mg/ml mix will be given throughout the duration of their epidural analgesia.
2. Rectus Sheath Block - 20 mL of liposomal bupivacaine diluted with 40 mL of 0.125% bupivacaine and 40 ml of injectable saline for a total of 100 mL. The 100 mL will be injected into 4 locations below the rectus abdominis muscle.
3. Surgeon infiltration with Liposomal Bupivacaine (LB) – 20 mL of liposomal bupivacaine diluted with 40 mL of 0.125% bupivacaine and 40 ml of injectable saline for a total of 100 mL. The 100 mL will be injected throughout the incision site by the surgeon at the end of surgery, prior to abdominal wall closure.
4. Surgeon infiltration with Standard Bupivacaine (SB) – 60ml of 0.5% bupivacaine will be diluted with 40ml of saline for a total of 100ml. The 100 mL will be injected throughout the incision site by the surgeon at the end of surgery.

Randomization will be performed using Research Randomizer. The primary investigator will inform the person doing the block as to what group the patients are randomized to

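### Postoperative creatinine is compared with no pre-operative value and no named time point: unbiased under randomisation, but less precise than it could be and unable to show a rise within a patient

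*Combined protocol and SAP*

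**What the plan says.** Creatinine appears in Section 2.0, in the Study procedures part of Section 4.0, and twice in Section 7.0, each time only as a post-operative quantity. Section 2.0 reads "We will also measure time to first flatus, postoperative creatinine, incidence of hypotension". The analysis sentence in Section 7.0 is "Time to first flatus, postoperative creatinine, and LOS will be compared between the groups using one-way ANOVA", at the general level set there: "A 5% significance level will be used for all comparisons".

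On timing, the Study procedures close their list of measurements with "All these parameters will be measured at 1, 24, 48, 72, and 96 hours after the cystectomy". All of these times are after surgery, and Section 7.0 does not say which value enters the ANOVA.

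The list that contains creatinine does give one outcome a within-patient reference: "incidence of hypotension (defined as BP decrease of more than 20% from morning of surgery". Creatinine has none. The planned baseline comparison covers demographic data only, and the exclusion criteria in Section 3.0 name no renal criterion.

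**The concern.** Creatinine differs between patients before any anaesthetic technique is applied. Without the pre-operative value, two things are lost.

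- **Precision.** The part of the post-operative spread that was already present before surgery stays in the error term, although it could be removed cheaply.
- **Interpretation.** A hypothetical patient stable at 2.0 mg/dL scores worse than one who goes from 0.7 to 1.4 mg/dL, yet only the second has changed. No test on post-operative values alone can separate the two.

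There is also a gap in specification. If creatinine is taken at five times, the analyst must choose one value or a summary, and nothing fixes that choice before the data are seen. Pain, satisfaction and opioid use are given a repeated-measures analysis; creatinine is not.

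**Working it through.** **The plan's own figure.** The only power statement is for VAS: 80% for a ratio of means of 1.5 with 40 per group, where the coefficient of variation of the "score at 48 and 72 hours is estimated to be 0.70", "assuming two-sided tests each conducted at a 5% significance level". On the log scale, SD = sqrt(ln(1 + 0.70²)) = 0.6315 and the difference is ln 1.5 = 0.4055. Power is 0.819 by the normal approximation and 0.809 by noncentral t, so the figure reproduces. It does not bear on creatinine, for which no power is stated.

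**Inputs for creatinine.**

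- Arm size: "A total of 160 subjects will be randomized by a computer program into four groups (40 in each group" (Section 4.0).
- Two-sided 5% level (Section 7.0).
- Correlation r between pre- and post-operative creatinine on the analysis scale: not in the documents. Assumed 0.6 to 0.9, with 0.5 added as a pessimistic case.

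**Unadjusted pairwise comparison.** The difference detectable with 80% power is (1.960 + 0.842) × sqrt(2/40) = 2.802 × 0.2236 = 0.63 SD. Power for a true difference of 0.5 SD is Φ(0.5/0.2236 − 1.960) = Φ(0.276) = 0.61.

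**Adjusted for the pre-operative value.** The residual SD is multiplied by f = sqrt(1 − r²). The detectable difference becomes 0.6265 × f. Power for 0.5 SD becomes Φ(0.5/(0.2236 f) − 1.960). The unadjusted arm size of equal precision is 40/(1 − r²), rounded up.

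| r | Variance explained, r² | f | Detectable difference (SD) | Power for 0.5 SD | Equivalent unadjusted n per arm |
|---|---|---|---|---|---|
| 0.5 | 0.25 | 0.87 | 0.54 | 0.73 | 54 |
| 0.6 | 0.36 | 0.80 | 0.50 | 0.80 | 63 |
| 0.7 | 0.49 | 0.71 | 0.45 | 0.88 | 79 |
| 0.8 | 0.64 | 0.60 | 0.38 | 0.96 | 112 |
| 0.9 | 0.81 | 0.44 | 0.27 | 0.999 | 211 |

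A simple change score does less well. Its detectable difference is 0.6265 × sqrt(2(1 − r)): 0.63 SD at r = 0.5 (no gain over raw values), 0.56 at 0.6 and 0.28 at 0.9.

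**Is the unadjusted test valid?** Four arms of 40 were simulated with normal data, 4,000 runs per setting, at r = 0.5, 0.7, 0.8 and 0.9. The unadjusted one-way ANOVA rejected a true null in 4.8% to 5.7% of runs. The Monte Carlo standard error is sqrt(0.05 × 0.95/4000) = 0.34 percentage points, so this agrees with 5%. A true 0.5 SD shift in one arm was estimated as 0.50 at every r. Power for that shift was 61% to 62% unadjusted, against 75%, 90%, 97% and above 99.9% with ANCOVA.

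**Chance imbalance.** The difference in mean pre-operative creatinine between two arms of 40 has standard error sqrt(2/40) = 0.22 SD, a 95% range of ±0.44 SD. At r = 0.8, an imbalance of 0.44 SD moves the post-operative difference by 0.8 × 0.44 = 0.35 SD. The 5% test allows for this on average over randomisations. In the trial actually run, it could be neither seen nor corrected without the pre-operative value.

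**The case against.** The strongest reply is that the analysis is valid. Arms are randomised, so expected prior kidney function is equal, and the simulation confirms both the error rate and the lack of bias. This stands in full. A reader might infer that the arm comparison mainly reflects prior kidney function. That treats spread between patients as if it were a difference between arms. Even as a statement about variance, prior function explains more than half only if r exceeds sqrt(0.5) = 0.71, and the documents give no r. Eligibility of ASA classes 1 to 4 is not a renal measure and does not supply one.

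A reader might also infer that the outcome cannot show injury at all. That holds for the individual patient only. A shift in arm means of about 0.63 SD is still detectable with 80% power.

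Third, the documents never call creatinine a renal-injury or safety endpoint. The stated secondary hypotheses concern satisfaction, nausea and sedation. Adverse events are reported separately (Section 5.0), and an independent group monitors outcome and adverse event data. This stands too, and it limits the weight of the point.

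Fourth, the five-times schedule may not be meant for creatinine. The sentence also covers length of stay and time to first flatus, which cannot be measured five times, and Sections 2.0 and 7.0 list creatinine without times. That is fair, but the analysed value is unnamed on either reading.

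None of these replies supplies a pre-operative value. The transformation clause in Section 7.0 deals with skewness, not with baseline.

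**Conclusion.** The point holds as one of precision and specification on a secondary outcome with no hypothesis. The planned comparison is unbiased with a correct type I error, but it uses neither a pre-operative value nor a named post-operative one, and it cannot separate a new rise from a long-standing high level in the same patient.

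The size depends on an assumed correlation. Over 0.6 to 0.9, adjustment is worth as much precision as raising each arm from 40 to between 63 and 211 patients. At 0.5 the equivalent is still 54. These figures are for a generic pair of pre- and post-operative values; a peak value may correlate differently. No conclusion on the primary outcome is affected. The case for acting is the low cost, not a threat to the trial.

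**What to change.** - **Baseline.** Abstract the last pre-operative creatinine from the medical record and add it to the data collected in Sections 2.0 and 4.0. This assumes that a value is on file before major surgery; no new blood test is needed. It can be done for patients already enrolled, but should be finished while identifiers are still held, since Sections 8.0 and 9.0 provide for their destruction three years after completion.
- **Outcome.** Name one post-operative value in Section 7.0 before analysis: for example a fixed time point before 96 hours, or the peak over a window that nearly all patients complete. A peak through 96 hours would be uneven, because Section 7.0 accepts missing 96-hour data after early discharge.
- **Analysis.** For creatinine, replace the one-way ANOVA with ANCOVA of log creatinine on arm, adjusted for log pre-operative creatinine. Report the arm differences as ratios with 95% confidence intervals.
- **Optional.** Give a descriptive count per arm of patients whose creatinine rises relative to their own baseline, by a threshold that the investigators set in advance.

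The cost is one extra data field, a revised sentence in Section 7.0 and a small amount of analysis work. There is no change to sample size, visits or patient burden.

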**[name]**  
**Medical Student, Indiana University School of Medicine**

**Version 5.0 10-21-19**

## 1.0 Background

Indiana University Hospital is a large academic health center that performs a large number (~180) of cystectomies per year. Cystectomy is a urologic procedure that involves the radical removal of the bladder, with subsequent need for urinary tract reconstruction. The reconstruction requires harvesting of portions of the small and/or large bowel, and can be in the form of an ileal conduit, orthotopic bladder replacement, or continent urinary reservoir such as an "Indiana Pouch". The postoperative course usually spans on average a 7-day inpatient hospital stay, with the majority of the issues surrounding management of postoperative pain and subsequent ileus. Currently, there is no standard of pain control in cystectomy, though adjunctive mechanisms of analgesia are often utilized to decrease opioid usage. Opioid use has long been associated with postoperative ileus, nausea and vomiting, aspiration, prolonged hospital stay, and several other side effects. Postoperative pain may also decrease patient satisfaction while increasing length of hospital stay and hospital costs. Without a standard practice for postoperative pain control in cystectomy, our study aims to compare thoracic epidural versus rectus sheath block versus surgeon infiltration of local anesthesia for cystectomy. With studies indicating improvements in perioperative outcomes for all three techniques, we believe we should compare these three methods for possible incorporation of the best technique for our enhanced recovery after surgery (ERAS) protocol for cystectomy. This will be done by collection of post-operative pain scores (VAS) at both resting and with movement. The VAS (Visual Analog Scale) pain scores will be measured at 24, 48, 72 and 96 hours under an advanced recovery perioperative care pathway.

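### Time to first flatus is a time-to-event outcome analysed by one-way ANOVA, with no end of recording stated and no value for patients without observed flatus

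*Combined protocol and SAP*

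**What the plan says.** The analysis is set in section 7.0: "Time to first flatus, postoperative creatinine, and LOS will be compared between the groups using one-way ANOVA". The same section allows a transformation or a nonparametric test if the distribution calls for it.

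The timing of flatus recording has to be pieced together:

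- The study procedures in section 4.0 say "We will also measure time to first flatus, postoperative creatinine" within a longer list, then close with "All these parameters will be measured at 1, 24, 48, 72, and 96 hours after the cystectomy".
- Section 7.0 lists flatus again in a sentence that ends "activity will also be recorded daily". It is unclear whether daily recording covers flatus or only ambulation, and no last day is given.
- Section 1.0 says "The postoperative course usually spans on average a 7-day inpatient hospital stay", which is well beyond 96 h.
- On early discharge, section 7.0 says "If the patient is discharged within 96 hours, every effort will be made to obtain data points" and does not count missing points as deviations. Section 6.0 allows withdrawal at any time.

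The documents do not say when flatus recording ends, or what is entered for a patient with no flatus seen by then. Ileus is a separate binary outcome analysed by logistic regression, and it is not defined.

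**The concern.** ANOVA needs a number for every patient. A patient still without flatus when recording stops has only a lower bound. With no rule for that case, the usual software default is to omit the patient. The omission depends on the outcome itself, because the longest times are the ones lost. If one arm is uniformly slower it loses more patients, so the observed difference shrinks and power falls.

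The permitted fallbacks deal with the shape of the distribution. A log transformation cannot supply an absent value, and a rank test that omits the same patients has the same defect. A rank test helps only if patients without flatus are given the worst rank, and the plan does not say so.

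Bowel recovery matters to this trial. Section 1.0 describes the hospital course as having "the majority of the issues surrounding management of postoperative pain and subsequent ileus", and section 2.0 names ileus among the aims.

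**Working it through.** **The plan's own figure.** The only power statement concerns VAS: 80% for a ratio of means of 1.5, coefficient of variation 0.70, 40 per group, two-sided 5%. On the log scale the SD is √ln(1 + 0.70²) = 0.631. Then ln 1.5 / (0.631 × √(2/40)) = 0.405/0.141 = 2.87, and Φ(2.87 − 1.96) ≈ 82%. The stated 80% is reproduced. It says nothing about flatus, for which the documents give neither times nor power.

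**Assumed inputs for flatus.** Lognormal times with log SD σ = 0.5; median 60 h in one arm and 80 h in the other three; 40 per arm (section 4.0); two-sided 5% (section 7.0). Recording ends at W = 96 h (last scheduled time, section 4.0) or W = 168 h (the 7-day average stay, section 1.0).

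**Formulas.** With median m and z = ln(W/m)/σ:

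- full mean = m·exp(σ²/2)
- share without flatus by W = 1 − Φ(z)
- mean of the times actually seen = full mean × Φ(z − σ)/Φ(z)

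**True difference.** 60 × 1.1331 = 67.99 h and 80 × 1.1331 = 90.65 h, so 22.7 h.

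**Recording to 96 h, patients without flatus dropped.**

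- m = 60: z = 0.940, 17% without flatus, mean seen 67.99 × 0.6700/0.8264 = 55.12 h.
- m = 80: z = 0.365, 36% without flatus, mean seen 90.65 × 0.4462/0.6423 = 62.97 h.
- Difference seen: about 7.8 h, or 35% of the true difference.

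**Recording to 168 h, patients without flatus dropped.**

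- m = 60: z = 2.059, 2% without flatus, mean seen 67.99 × 0.9405/0.9803 = 65.23 h.
- m = 80: z = 1.484, 7% without flatus, mean seen 90.65 × 0.8374/0.9311 = 81.53 h.
- Difference seen: 16.3 h, or 72% of the true difference.

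**Power, by simulation of four-arm trials.** Repeated runs differ by a few percentage points; ranges are shown where they do.

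| Analysis | To 96 h | To 168 h |
|---|---|---|
| ANOVA, no-flatus patients dropped | about 35% | about 60% |
| ANOVA on log times, same patients dropped | – | 66% to 69% |
| Kruskal-Wallis, same patients dropped | 33% to 34% | – |
| Kruskal-Wallis, no-flatus patients tied last | about 71% | – |
| Log-rank, censored at end of recording | 67% to 71% | 69% to 71% |

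**Faster recovery, medians 48 v 64 h, same σ.** To 96 h: 8% v 21% without flatus, 18.1 h seen as 8.8 h, power 46% to 48% against 68% to 70% for log-rank. To 168 h: 0.6% v 2.7% without flatus, 15.3 of 18.1 h seen, power 64% to 66% against 68% to 69%.

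**Wider range at 96 h.** Medians from 48 v 60 h to 72 v 96 h, log SD 0.4 and 0.6. Between 4% and 50% of an arm has no flatus by 96 h. Dropping these patients leaves 21% to 65% of the true mean difference (for example 6.1/28.7 and 8.4/13.0). Power is 12% to 71% with dropping, 30% to 96% with log-rank, and 30% to 97% with Kruskal-Wallis and last-rank ties. With equal medians, every method keeps a type I error of about 5%.

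**The case against.** The strongest reply is that the plan does not say what the worst case needs it to say. Five stronger readings are tempting, and the documents do not support them.

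1. *Flatus is recorded only to 96 h.* The closing sentence of the study procedures also covers LOS, which is taken from the discharge date and cannot stop at 96 h. The average stay is 7 days, and daily recording may apply. The end of recording is unstated, and at 168 h most of the power loss disappears, especially on the log scale that the plan already allows.
2. *The plan drops patients without flatus.* No such rule is written. Dropping is only what the software does with an empty value.
3. *The patients dropped are the ileus cases.* This is an inference. Ileus is undefined and analysed separately, so those patients are not lost from every bowel-function comparison.
4. *The bias always runs toward no difference.* That follows from an arm being uniformly slower. An arm with earlier flatus among those who pass it, but more patients who never do, would look better after dropping.
5. *Nonparametric tests cannot help.* They can, if patients without flatus take the worst rank; power then matches log-rank.

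Flatus is also one of many secondary outcomes, with no stated hypothesis or power.

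These points limit the size and certainty of the concern. They do not remove it: the named method has no place for a patient without an event, and the handling would be settled only after data are in hand.

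**Conclusion.** The point holds as a mismatch between outcome and method, and it should be corrected before analysis. One-way ANOVA is prescribed for a time to an event, the only written schedule covering it ends at 96 h without clearly being the limit of recording, and no rule covers patients without observed flatus.

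The loss depends mainly on when recording ends. In the 60 v 80 h example it runs from severe at 96 h (about one third of the difference seen, power roughly halved) to modest at 168 h (about 72% of the difference seen, power about 10 percentage points lower on the raw scale and a few points lower or less on the log scale).

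These figures rest on assumed lognormal times, exact recording of the time of flatus, and default omission of patients without flatus. The documents can confirm none of these. The direction of bias is likewise conditional on one arm being uniformly slower. The consequence is confined to a secondary outcome; the primary VAS analysis and the sample size are unaffected.

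**What to change.** In section 7.0, take time to first flatus out of the one-way ANOVA sentence and specify:

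- Kaplan-Meier curves by arm, a log-rank test across the four arms, and Cox hazard ratios for epidural versus each other arm;
- when flatus recording ends, with the section 4.0 schedule and the daily-recording sentence in section 7.0 made consistent with it;
- censoring at the last flatus assessment, discharge or withdrawal without flatus, with the number censored for each reason reported by arm.

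A prespecified Kruskal-Wallis test with patients without flatus given the worst rank is an acceptable alternative.

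The cost is SAP wording and a censoring indicator in the database; no new data are needed beyond the date and time of the last flatus assessment. The small downside is that results are reported as medians and hazard ratios instead of mean differences.
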